6.7.7.6 Pregnancy Test

Female of childbearing potential will have a serum pregnancy test taken at screening and Study Day -1 and then urine pregnancy tests monthly (week 4, 8 and 12) and at study completion, week 14. The outcome of the test will be reported as “positive” or “negative” in the CRF.

7 Quality control and quality assurance

This study will be conducted in compliance with this protocol, study specific procedures, Sobi’s and the CRO’s SOPs, the ICH Guideline for GCP (1), and applicable regulatory requirements.

The sponsor will systematically review the study quality management to identify, evaluate and control risks to study critical processes and data which would affect subject safety and reliability of study data.

The Sponsor will establish a systematic, prioritized, risk-based approach to monitoring and has chosen a combination of on-site and centralized monitoring.

Monitoring visits to the study site will be performed periodically during the study, to help ensure compliance with the protocol, study specific procedures and applicable regulatory requirements. Source documents will be reviewed for verification of agreement with data in CRFs. All subject informed consent forms will be reviewed. The investigator or institution guarantees access to source documents by Sobi, its representatives, and appropriate regulatory agencies.

The study site may be subject to a quality assurance audit by Sobi or its representatives, as well as inspection by appropriate regulatory agencies.

It is important that the investigator(s) and the(ir) relevant personnel are available during the monitoring visits and possible audits and that sufficient time is devoted to the process.

8 Statistical plan

8.1 Determination of sample size

This is a phase I study to evaluate the pharmacokinetics and pharmacodynamics of emapalumab in healthy Japanese subjects following single dose administration of emapalumab.

No formal sample size calculation was made but the sample size was chosen based on previous experience in phase I studies. Also, 6 subjects receiving emapalumab are considered sufficient, considering the inter-subject variability in the PK results in the NI-0501-03 study and 2 placebo is considered a reasonable number of subjects. In study NI-0501-03 CV for inter-subject variability was within 30% for PK parameters such as Cmax and AUC % based on 4 subjects at a dose level of 1 mg/kg emapalumab.

8.2 Definition of study populations

All analyses will be conducted on the modified intention-to-treat (mITT) population which will comprise all randomized subjects who received an infusion of IMP and have at least one blood draw to determine PK and PD.

The Safety population will comprise of all patients who received an infusion of IMP.

8.3 Overall statistical and analytical plan

8.3.1 General statistical issues

A study specific statistical analysis plan (SAP) containing a detailed description of all analyses to be conducted will be developed and finalized prior to database lock. Suitable tabular and graphical summaries will be prepared for individual data and for appropriate summary statistics, and all data will be listed. No formal statistical hypothesis testing will be performed. All endpoints will be summarized with descriptive statistics and presented individually in listings.

8.3.2 Demographics and baseline characteristics

Demographics and baseline characteristics will be summarized using descriptive statistics.

8.3.3 Analysis related to primary objective

8.3.3.1 Analysis of pharmacokinetic parameters

The pharmacokinetic analysis will primarily be conducted using non-compartmental procedures and results of PK parameter will be presented by descriptive statistical methods.

PK modelling may also be used based on naïve pooled compartmental modeling and/or non-linear mixed effects modeling compartmental analysis may be used as deemed appropriate.

PK results may be compared with other studies e.g. study NI-0501-03, but will not be presented in the report for this study.

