4.2 Study rationale

The primary objective of the study is to evaluate PK and PD in Japanese Healthy subjects, and the results of this study will be compared with the results of the non-Japanese phase I single-dose study (NI-0501-03). As there is no experience using emapalumab in Japanese subjects it is important to compare the PK and PD of emapalumab data between Japanese and non-Japanese subjects to confirm comparable PK and PD properties.

4.3 Rationale for Herpes Zoster prophylaxis.

One Healthy Volunteer reported Herpes zoster infection of moderate intensity after a single emapalumab infusion of 3 mg/kg during the NI-0501-03 study. The event resolved upon treatment and was considered related to emapalumab (IFN γ neutralization suspected to favor emergence of the infection).

Patients treated with emapalumab are recommended prophylactic treatment with valaciclovir to prevent reactivation of Herpes zoster. Studies with valaciclovir as Herpes zoster prophylaxis have been performed in Japan with prophylactic treatment up to one year (26). The benefit of valaciclovir prophylaxis is judged to exceed the risks with Herpes zoster reactivation.

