6.6.3 Methods of assigning subjects to treatment groups

A single intravenous dose of 1 mg/kg is considered relevant for this Phase 1 study in Japanese healthy subject to bridge to the global Phase 1 study NI-0501-03 where single dose administration of 0.01, 0.1, 1 and 3 mg/kg were administered.

Because the PK of emapalumab in healthy adults is linear, one dose level is sufficient for a comparison between Japanese and non-Japanese. Also, a single dose is sufficient to compare PK between Japanese and non-Japanese, since the PK of emapalumab does not show any time-dependency upon repeated-dose since administration.

The global Phase 1 study (NI-0501-03) in 20 healthy adult volunteers investigated the safety, tolerability and PK profiles of single IV administrations of emapalumab. During this study 6 subjects received placebo, while 3, 3, 4, and 4 subjects (in total 14 subjects) received emapalumab doses of 0.01, 0.1, 1, and 3 mg/kg, respectively. All IMP infusions were uneventful, and most AEs were singular occurrences and no trend in relation to increasing emapalumab dosage was observed.

The PK analysis of emapalumab in the NI-0501-03 study revealed the expected profile for an IgG1 with a long half-life (around 22 days), a slow clearance (≤ 0.1 mL/kg/hr) and a low volume of distribution (<65 mL/kg on average). The serum concentrations following 1 mg/kg were

pharmacologically relevant since Cmax (32 200 ng/mL) was approximately 50 times the IC50 (603 ng/mL) for significant neutralization of IFN γ .

Considering the scaling factor from the Non-human primate to human (x0.32). 30 mg/kg (NO AEL) which was very well tolerated in monkeys, with no adverse clinical signs or organ toxicity reported, correspond to a HED of 10 mg/kg, therefore the 30 mg/kg in monkey is 10-fold higher than the starting dose in human of 1 mg/kg

Taken these aspects into account, a single intravenous dose of 1 mg/kg emapalumab has been selected for the Phase 2-3 study in pHLH thus this dose is selected also for this study in Japanese healthy subjects.

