8.3.3.2 Analysis of pharmacodynamic parameters

All PD data will be summarized using appropriate graphical and tabular presentations.

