## 2 Introduction

This Statistical Analysis Plan (SAP) describes the planned analysis and reporting for the Sobi protocol Sobi.emapalumab-102 (A randomized, double-blinded, placebo-controlled, single center, phase I study to evaluate pharmacokinetics, pharmacodynamics and safety of emapalumab after a single intravenous dose in Japanese healthy volunteers.).

This phase I study is being completed to assess the pharmacokinetics, pharmacodynamics and safety of emapalumab in healthy Japanese subjects following a single i.v. dose of emapalumab.

The purpose of this SAP is to outline the planned analyses to be completed to support the Clinical Study Report (CSR) for protocol Sobi.emapalumab-102. The planned analyses identified in this SAP will be included in regulatory submissions and/or future manuscripts. Also, exploratory analyses not necessarily identified in this SAP may be performed to support the clinical development program. Any post-hoc, or unplanned, analyses not identified in this SAP will be clearly identified in the respective CSR.

The structure and content of this SAP provides sufficient detail to meet the requirements identified by the FDA and International Council on Harmonisation of Technical Requirements for Registration of Pharmaceuticals for Human Use (ICH): Guidance on Statistical Principles in Clinical Trials. All work planned and reported for this SAP will follow internationally accepted guidelines, published by the American Statistical Association and the Royal Statistical Society, for statistical practice.

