## 6 Sample size determination

This is a phase I study to evaluate the PK and PD of emapalumab in healthy Japanese subjects following single dose administration of emapalumab. No formal sample size calculation was made but the sample size was chosen based on previous experience in phase I studies. Also, 6 subjects receiving emapalumab are considered sufficient, considering the inter-subject variability in the PK results in the NI-0501-03 study, and 2 subjects receiving placebo is considered a reasonable number. In study NI-0501-03 the CV for inter-subject variability was within 30 % for PK parameters such as  $C_{max}$  and AUC % based on 4 subjects at a dose level of 1 mg/kg emapalumab.

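### The rationale promises a PK and PD comparison with NI-0501-03, but the analysis plan leaves it optional, PK-only and outside the report, with no measure, comparator or reporting document fixed

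*Protocol*

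**What the plan says.** **Rationale.** Protocol 4.2 states that "the results of this study will be compared with the results of the non-Japanese phase I single-dose study (NI-0501-03"), and that comparing PK and PD between Japanese and non-Japanese subjects is important "to confirm comparable PK and PD properties". Protocol 6.6.3 presents the 1 mg/kg dose as a bridge to that study. It argues from linear PK that "one dose level is sufficient for a comparison between Japanese and non-Japanese".

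**PK analysis.** Protocol 8.3.3.1 says: "PK results may be compared with other studies e.g. study NI-0501-03, but will not be presented in the report for this study". Protocol 6.7.5.2 allows, but does not require, PK modelling pooled with NI-0501-03 data.

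**PD analysis.** Protocol 8.3.3.2 says only: "All PD data will be summarized using appropriate graphical and tabular presentations". Protocol 6.7.6.2 and SAP 14.2 describe the biomarkers within this study.

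**SAP.** Protocol 8.3.1 describes the SAP as a document "containing a detailed description of all analyses to be conducted will be developed and finalized prior to database lock". The SAP mentions NI-0501-03 only in its design text (4.1) and in the sample size section (6), where 6 subjects are judged enough "considering the inter-subject variability in the PK results in the NI-0501-03 study". SAP 2 adds that "exploratory analyses not necessarily identified in this SAP may be performed to support the clinical development program".

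**Objective.** The formal primary objective (Protocol 5.1, SAP 3.1) is to evaluate PK and PD in healthy Japanese subjects. It does not mention a comparison.

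**The concern.** Between Protocol 4.2 and 8.3.3.1 the comparison changes in three ways: *will* becomes *may*, PK and PD becomes PK alone, and the result is kept out of this study's report with no other document named. The team could therefore follow the analysis plan exactly and never address the question that 4.2 gives as the reason for the study.

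The NI-0501-03 results are already known. What can still be protected is the choice of measure and comparator (the 1 mg/kg group, several dose groups, or a pooled model), provided it is fixed before this study's data are unblinded. At present nothing fixes it.

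A related problem affects the PD side. In NI-0501-03 the mean total IFNγ at 1 mg/kg peaked at Week 8, and SAP Table 1 has no PD analysis time point near that visit.

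**Working it through.** **1. The passages side by side**

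| Question | Protocol 4.2 | Protocol 8.3.3 | SAP |
|---|---|---|---|
| Is PK compared with NI-0501-03? | Yes, committed | Optional, not in this report | Not specified |
| Is PD compared with NI-0501-03? | Yes, committed | Not mentioned | Not specified |
| Comparator dose group | Not stated | Not stated | Not stated |
| Measure or criterion | Not stated | Not stated | Not stated |
| Where reported | Not stated | Not in this report | Not stated |

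**2. What a PK comparison could show**

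The documents give no power, margin or precision figure, so there is none to reproduce. Inputs:
- 6 subjects on emapalumab here (Protocol 6.6, SAP 4.3).
- 4 subjects at 1 mg/kg and 14 on emapalumab in total in NI-0501-03 (Protocol 4.1.2.3).
- Observed CVs within 30% for parameters such as Cmax and AUC, from 4 subjects (Protocol 8.1).
- CVs of 20% and 40% are my assumptions, to show a range.

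Log-scale SD: σ = √ln(1 + CV²) = 0.1980, 0.2936 and 0.3853 at CV 20%, 30% and 40%.

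CI factor for a geometric mean ratio: exp(t × σ × √(1/n₁ + 1/n₂)), taking the observed SD to equal σ.

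- 6 versus 4: √(1/6 + 1/4) = 0.6455, with t(0.95; 8 df) = 1.860. At CV 30%: exp(1.860 × 0.2936 × 0.6455) = 1.42.
- 6 versus 14, dose-normalised, assuming equal CV at all doses: √(1/6 + 1/14) = 0.4880, with t(0.95; 18 df) = 1.734. At CV 30%: exp(1.734 × 0.2936 × 0.4880) = 1.28.

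| CV | 90% CI around an observed ratio of 1, 6 vs 4 | 6 vs 14 |
|---|---|---|
| 20% (assumed) | 0.79 to 1.27 | 0.85 to 1.18 |
| 30% (stated ceiling) | 0.70 to 1.42 | 0.78 to 1.28 |
| 40% (assumed) | 0.63 to 1.59 | 0.72 to 1.39 |

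At the 95% level that the SAP uses for geometric means, the factors at CV 30% are 1.55 for 6 vs 4 (t = 2.306) and 1.35 for 6 vs 14 (t = 2.101).

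The 30% is a ceiling on the CVs observed in 4 subjects and does not bound the true CV. With 3 df, the 95% interval for a true SD runs from √(3/χ²(0.975)) = 0.57 to √(3/χ²(0.025)) = 3.73 times its estimate. The documents give no individual CV estimate to apply this to, so it serves only as a caution. No such calculation is possible for PD, because no PD variability is given.

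**3. The PD visits**

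- SAP Table 1: the Week 6 window ends on Day 44 and the next PD window (Week 14) starts on Day 96, a distance of 96 − 44 = 52 days. The Week 8 window (Days 54 to 58) is marked for PK only.
- Protocol synopsis: PK/PD sampling includes Week 10.
- Protocol Table 4, which Protocol 6.7.6 makes the PD schedule: as far as the table can be read in text form, PD appears to be marked at Weeks 8, 10 and 12.
- Protocol 4.1.2.3: mean total IFNγ at 1 mg/kg reached its maximum, 1013.6 pg/mL, at Week 8.

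The SAP and the synopsis disagree whatever Table 4 shows.

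**The case against.** **The objective does not require a comparison.** This stands. A reader might infer that the study cannot meet its primary objective. The documents do not support that: the objective is to evaluate PK and PD in Japanese subjects, and the planned descriptive analyses do so.

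**Reporting elsewhere is legitimate.** This also stands. The SAP supports the study report, 8.3.3.1 keeps the comparison out of that report, and SAP 2 allows further analyses, so the SAP's silence largely follows from that decision and is not a separate breach. What remains is that no other document is named, and a permission to explore is not a plan.

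**A PD comparison is stated.** A reader of 8.3.3.2 and the SAP might conclude that the protocol has none. Protocol 4.2 does state one; it is unspecified, not absent.

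**One dose level and 6 versus 4.** Protocol 6.6.3 rests the single dose level on linear PK, and the comparison is the purpose it serves. The same linearity makes a dose-normalised or pooled comparison reasonable, which is why the 6 versus 14 figure is shown. It narrows the interval but does not turn a description into a confirmation.

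**The PD schedule evidence is uneven.** The PK row of Table 4 carries the same number of marks as the PD row. Read literally, that implies a 12-hour PK sample, which Protocol 6.7.5 and SAP Table 1 do not list. Table 4 is therefore weak evidence alone. The Week 8 peak is a mean in a 4-subject dose group, and at 3 mg/kg a nearly equal maximum (1011.2 pg/mL) came at Week 4, which this study samples. So a reader should not infer that the IFNγ peak will be missed, or that no PD samples are taken at Weeks 8 to 12.

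**The parameters are already fixed.** True, as are geometric means with 95% CIs (SAP 8.3.1), so a later ratio is simple arithmetic. Prespecification mainly protects the choice of comparator and of measure.

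**Conclusion.** The concern holds as a conflict between the study rationale and the analysis plan. Protocol 4.2 commits to a PK and PD comparison with NI-0501-03 intended to confirm comparability. The analysis sections make it optional for PK, leave it unspecified for PD, and name neither comparator group nor reporting document. The plan should be corrected, but the formal objective is not at risk.

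At CV 30% a 90% CI would span about 0.70 to 1.42 around an observed ratio of 1 for 6 versus 4, or 0.78 to 1.28 for a dose-normalised 6 versus 14. These figures assume log-normal data and a common CV in both studies (and across doses for the second); the true CV may be above or below 30%. With no criterion for comparability, *confirm* is too strong. This is not an argument that the study is undersized or needs a test or a margin, since the plan is openly descriptive.

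The disagreement over PD visits between SAP Table 1 and the synopsis is a separate, smaller point. It matters here because it covers the visit at which the comparator's mean IFNγ peaked.

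**What to change.** 1. **Protocol 8.3.3.1.** Replace the sentence with a commitment, for example: *PK and PD results will be compared descriptively with NI-0501-03. The comparison will be specified before database lock in [SAP section or named bridging report] and reported there.*
2. **Measure and comparator.** Specify the geometric mean ratio (this study over NI-0501-03) with a CI on the log scale for Cmax, AUCinf and weight-normalised CL, against the 1 mg/kg group. Name the dose-normalised or pooled comparison as a supporting analysis. Use no test and no margin. State the confidence level: 90% is a convention used here for illustration, and 95% would match SAP 8.3.1.
3. **PD.** Reconcile the PD visits in SAP Table 1 with Protocol Table 4 and the synopsis, so that any PD data collected at Weeks 8 to 12 are summarised. Show total IFNγ from the two studies side by side at common visits.
4. **Protocol 4.2.** Change the aim from confirming comparability to describing PK and PD alongside the earlier study.

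**Cost.** Wording in two protocol sections, a short specification, a correction to one SAP table, and one or two output tables. No new subjects or procedures are needed. SAP Table 4 already derives CL by mg/kg dose. Precision will be modest. The documents do not show the NI-0501-03 assay or PK sampling schedule, so between-study differences must be noted as a limitation, and the PD comparison may reduce to total IFNγ, the only NI-0501-03 biomarker result they report.

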8.3.3.2 Analysis of pharmacodynamic parameters

All PD data will be summarized using appropriate graphical and tabular presentations.

8.3.4 Analysis related to secondary objective

8.3.4.1 Adverse events

Reported AEs during the study will be coded using MedDRA. The incidence of AEs will be summarized in frequency tables by IMP, system organ class, preferred term, relationship to IMP and maximum severity. Separate tabulations will be performed for serious and non-serious AEs.

8.3.4.2 Laboratory Parameters

Abnormal laboratory values will be listed and their incidence, severity and relationship to the IMP will be tabulated for the IMP groups. Change from baseline will be summarized by IMP group. Individual changes (shift tables), individual clinically significant abnormalities and severity grading (mild, moderate, severe) will also be presented.

8.3.4.3 Anti-drug antibodies

The number and percentage of patients with ADA at baseline and at the post-baseline assessment will be summarized.

8.3.5 Analysis of safety and tolerability data

8.3.5.1 Vital signs and physical Examination

Abnormal values from physical examination findings and vital signs will be summarized descriptively over time.

8.3.5.2 Infusion reactions

The incidence and severity of infusion related reactions will be analyzed (including the need for medication)

8.3.6 Interim analysis

No interim analysis will be performed.

8.3.7 Multiple comparison/multiplicity

As no formal hypothesis testing will be performed adjustment for multiple comparisons will not be applicable in this study.

8.3.8 Handling of missing data

No imputations of missing data will be performed.

9 Data collection, handling and record keeping

9.1 Data standards

Collection of data should be performed in the CDASH format, according to the CDISC. The standards should be used to the extent possible and/or required for the specific study/project. The minimum requirement of the CDISC standard is to collect all core variables specified as 'Required' in the Study Data Tabulation Model format.

9.2 Case report form

A CRF is required and should be completed for each included subject. In this study an electronic CRF will be used. The completed original CRFs are the sole property of Sobi and should not be made available in any form to third parties, except for authorized representatives of appropriate Regulatory Authorities, without written permission from Sobi.

It is the responsibility of the investigator to ensure completion and to review and approve all CRFs. CRFs must be signed electronically by the investigator. These signatures serve to attest that the information contained on these CRFs is correct. At all times, the investigator has final responsibility for the accuracy and authenticity of all clinical and laboratory data entered on the CRFs.

9.3 Source data

Subject source documents are the physician's subject records maintained at the study site. In most cases, the source documents will be the hospital's or the physician's chart. In those cases, the information collected on the CRFs must match those charts. In some cases, a portion of the source documents for a given subject may be the CRF.

A separate source document location agreement will be completed and signed by the principle investigator and the monitor before study start.

Source data should be attributable, legible, contemporaneous, original, accurate, and complete. Changes to source data should be traceable, should not obscure the original entry, and should be explained if necessary (e.g. via an audit trial).

9.4 Protocol Deviations

A protocol deviation is generally an unplanned excursion from the protocol that is not implemented or intended as a systematic change. The investigator is responsible for ensuring the study is conducted in accordance with the procedures and evaluations described in this protocol and must protect the rights, safety, and welfare of subjects. The investigator should not implement any deviation from, or changes of, the protocol, unless it is necessary to eliminate an immediate hazard to study subjects.

A protocol waiver is a documented prospective approval of a request from an investigator to deviate from the protocol. Protocol waivers are strictly prohibited.

For the purpose of this protocol, deviations requiring notification to the CRO are defined as any subjects who:

- Entered into the study even though they did not satisfy entry criteria;
- Developed withdrawal criteria during the study and not withdrawn;
- Received wrong treatment or incorrect dose;
- Received excluded concomitant treatment.

When a deviation from the protocol is identified, the investigator or designee must ensure the CRO is notified. The CRO will follow up with the investigator, as applicable, to assess the deviation and the possible impact to the safety and / or efficacy of the subject to determine subject continuation in the study.

The investigator and CRO must contact Sobi immediately if a deviation is discovered that significantly affects or has the potential to significantly affect human subject protection or the reliability of study results.

The investigator will also assure that deviations are reported and documented in accordance with IRB and applicable regulatory requirements.

